1. INTRODUCTION

Transcatheter aortic valve replacement (TAVR) has been performed with many various access approaches, however superiority to surgical aortic valve replacement was only seen in transfemoral access¹. Intravascular lithotripsy (IVL) for peripheral arterial disease (PAD) was first investigated in the DISRUPT PAD I and DISRUPT PAD II trials, which demonstrated that IVL resulted in a significant reduction in stenosis severity and minimal vessel injury in patients with severely calcified femoropopliteal disease^{2,3}. DISRUPT PAD III showed that peripheral IVL was safe and effective and could enable large-bore sheath advancement through calcified peripheral vessels⁴. Prior to these studies and IVL, heavily calcified iliofemoral arteries remained challenging for transfemoral access for TAVR. A case series previously reported outcomes on “hostile” iliofemoral arteries for TAVR, twelve patients required preparatory PTA prior to advancing the TAVR device, two patients failed the procedure due to common iliac perforation requiring stenting, both of which had severe circumferential calcifications⁵. IVL utilization to facilitate transfemoral access in patients undergoing TAVR with prohibitive iliofemoral vascular disease was shown to be advantageous by disrupting calcification and allowing for safe passage of the large-bore delivery sheaths⁶. This has allowed for the ability to expand the population eligible for TAVR. To our knowledge, there have not been any studies evaluating if Shockwave IVL reduced access site complications as the primary objective. The aim of our study is to evaluate this question.

2. RATIONALE

We believe that utilization Shockwave IVL of calcified femoral access site prior to large bore access will reduce complications and improve outcomes after large bore arterial access.

3. STUDY PLAN

3.1 Study Design

This is a prospective randomized/control trial pilot study to compare clinical outcomes of common femoral artery access in patients undergoing Transcatheter Aortic Valve Replacement (TAVR) at the University of Tennessee Medical. Specifically, we will compare patients utilizing the Shockwave model (M5) Intravascular Lithotripsy (IVL) prior to standard arterial access using the modified Seldinger technique to those utilizing the standard femoral artery access via the modified Seldinger approach without the utilization of intravascular lithotripsy in heavily calcified femoral arteries.⁷

3.2 Objectives

3.2.1 Primary Objective

The primary objective is to observe reduced access site complications in patients with heavily calcified common femoral arteries requiring TAVR.

3.2.2 Secondary Objectives

1. Determine the clinical outcomes between groups.
2. Distinguish extravasation post closure at the end of the procedure.
3. Compare the need for open vascular surgery between groups.

4. Examine PTA or Stents to the CFA to help hemostasis or local vascular complications between groups.
5. Number of Perclose devices used between groups.
6. Compare Bleeding/Hematoma between groups.
7. Examine the difference in hospital length of stay between groups.
8. Examine renal function post procedure
9. Difference in pain or numbness in the distal extremity between groups
10. Mortality related to complications from vascular closure site between groups.
11. Conversion to general anesthesia due to additional procedures required to address the CFA access site complications between groups.

3.3 Study Duration

We plan to enroll up to a total of 100 patients, 50 patients in each group. The total study duration will be approximately 12 months post IRB approval and study initiation. We will follow patients for 3 months post procedure for any adverse events; however, we would expect to see them within 3 days if there are events to occur.

3.4 Selection of Study Participants & Informed Consent

Patients at the UT Medical Center who meet the predefined inclusion and exclusion criteria will be enrolled after they provide consent to participate. The nature and purpose of the study will be explained to the patient by one of the investigators and the patient will be given a copy of the informed consent to review. The investigator or study coordinator will answer any questions which the patient may have prior to their signing the consent. The signed informed consent will be kept in the patient's research chart and a copy will be given to the patient. No study related interventions will be performed until after the patient signs the informed consent. The consent process will occur at an earlier date than the actual procedure to give patients plenty of time to review and ask questions.

3.4.1 Inclusion Criteria

1. >18 years of age
2. Patient with a diagnosis of severe aortic stenosis undergoing TAVR
3. Able to read and understand study procedures
4. Willing to participate and sign an ICF
5. Patients with > 90-degree arc of calcium at the large bore access site per CT documentation

3.4.2 Exclusion Criteria

1. Unable to understand study procedures
2. Unwilling to give consent
3. Patients with cognitive impairments that can affect their ability to give consent.
4. Unfavorable calcium distribution of femoral artery

3.5 Discontinuation of Subjects

An individual patient is to be withdrawn from the trial if any of the following criteria apply:

- The patient withdraws consent, without the need to justify the decision
- The patient is no longer able to participate for medical reasons (e.g., surgery, AEs, or other diseases)
- Decision by the PI to discontinue a specific patient for his/her safety (e.g., in case of SAEs)

Data of patients who discontinue or withdraw prior to enrollment will be entered in the study database and will be listed. Data of patients who discontinue or withdraw after enrollment will be documented and the reason for withdrawal will be recorded in the study record. The data will be included in the study database and will be reported.

4. STUDY PROCEDURES

4.1 Screening and Enrollment

Screening assessments will be completed by the study team on a day before the procedure to allow patients time to review and ask questions. Assessments will be initiated after the Informed Consent Form (ICF) Process. A study designee will present the study information to the patient. They will explain the purpose, risk, and benefits to the subject and present them with an IRB approved ICF. The potential participant will be given ample time to read the ICF and all questions and concerns from the subject will be addressed by a study team member. No procedures will be initiated prior to the subject signing and dating the ICF. After the subject signs the ICF, a copy will be given to them for their records. Participants will be informed that they can decline participation in the study without any effect on their health care. They can also withdraw their consent, including the consent to do various screening tests, at any time.

4.2 Datapoints/procedures to be collected/obtained:

- Informed Consent
- Medical History Review for Inclusion/Exclusion Criteria
- Concurrent Medication Review
- Pre-TAVR CT scan review
- Review of pre procedure laboratory results
- Demographics
- Pre-procedure consultation/progress notes
- Post procedure notes (consult, progress, discharge summary)
- Post procedure laboratory results and imaging
- Post discharge follow up office notes and vital signs

If subjects meet all I/E criteria, they will be Enrolled, and the following will be recorded

- Flow rates prior to and post procedures
- Documentation of extravasation post closure at the end of the procedure.
- If open vascular surgery occurred
- Number of perclose devices used

- Bleeding/Hematoma outcomes
- Hospital length of stay
- Renal function lab results post procedure
- Pain or numbness in the distal extremity post procedure
- Whether conversion to General Anesthesia was needed during procedure
- Review of post-procedure laboratory results
- Surgical/procedure reports
- Mortality
- Discharge summary
- Adverse event monitoring

4.3 Study Assessment Methods

4.3.1 Informed Consent Process

Patients at the UT Medical Center who meet the predefined inclusion and exclusion criteria will be enrolled after they provide consent to participate. The nature and purpose of the study will be explained to the patient by one of the investigators and the patient will be given a copy of the informed consent to review. The investigator or study coordinator will answer any questions which the patient may have prior to their signing the consent. The signed informed consent will be kept in the patient's research chart and a copy will be given to the patient. No study related interventions will be performed until after the patient signs the informed consent. The consent process will occur before the actual procedure day to assure the patient has plenty of time to review and ask questions.

4.3.2 Withdrawal of Consent

Patients may withdraw from the study at any time. Patients should make every attempt to complete the study as specified. Investigators should encourage patient treatment compliance and adherence. All deviations from the planned treatment schedule will be documented.

4.3.3 Study Intervention Administration

The patient will be randomized using a randomized generator to either Group 1 (intervention) or Group 2 (control).

Study approach will be administered by [name].

1. We will first obtain access on the Common Femoral Artery (CFA) contralateral to the planned large bore access.
2. We will use a 6 F sheath and an Omnipulse or similar catheter over an 0.035 Benson, Wholey or Advantage- glide wire.
3. We will then advance a 0.014 wire distal into the external iliac and remove the Omnipulse catheter.
4. Over the 0.014 wire, we will advance Shockwave 60 mm balloon sized to the distal CFA balloon and perform IVL of the contralateral CFA.
5. After completing shockwave IVL we will then access the CFA with Fluoroscopy/US guidance and preclose followed by placement of a large bore sheath.

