9. STATISTICAL METHODS AND DETERMINATION OF SAMPLE SIZE

9.1 Sample Size Determination

The researchers could not find an evidence-based measure of effect size from the existing literature. Therefore, this project will be considered a pilot study. The researchers believe there will at least be 10-20% reduction in complications associated with the treatment based on clinical experience. An *a priori* sample size calculation was performed using a 20% reduction, and with a two-tailed hypothesis, a power of 80%, and an equal allocation ratio to treatment arms, a total of $n = 100$ participants was generated. Therefore, the researchers plan on enrolling $n = 50$ participants in each treatment arm, totaling $n = 100$ participants. The effect size yielded from the final analysis will be used to power a future, larger trial between the two treatment arms.

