differences at baseline will be accounted for in the primary analysis using logistic regression. Chi-square or Fisher's Exact test will be performed to compare the treatment arms on distinguishing extravasation post-closure at the end of the procedure (yes/no), comparing the need for open vascular surgery (yes/no), utilizing a PTA/stent to help with hemostasis or local vascular complications (yes/no), bleeding/hematomas (yes/no), pain or numbness in the distal extremity (yes/no), mortality related to complications associated with the vascular closure site (yes/no), and conversion to general anesthesia due to additional procedures required to address CFA access site complications (yes/no). Cross-tabulation tables with frequencies, percentages, and associated OR with 95% CI will be reported and interpreted for all bivariate analyses of categorical, secondary outcomes. For count variables and non-normal continuous parameters (number of perclose devices, LOS, and serum creatinine), Mann-Whitney U tests will be performed to compare the two treatment arms. Medians and interquartile ranges will be reported and interpreted for the non-parametric analyses of the count and continuous parameters. Survival analysis will be performed using Kaplan-Meier in order to compare the two treatment arms on "time-to-event" outcomes. Mean and median times to events will be presented. Log-rank, Breslow, and Tarone-Ware tests will be used to compare the respective groups. Survival plots will also be graphed. All analyses will be performed using SPSS Version 29 (Armonk, NY: IBM Corp.) and statistical significance will be assumed at an alpha value of 0.05.

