11.1 Data Protection

Throughout the study, measures to ensure the privacy of information on study subjects will be maintained. All project investigators and staff have been trained in the use of human subjects in research and have received training in the new HIPAA regulations. Subjects and staff will be informed of the confidentiality of information and assured that data will be used only for statistical purposes in which the individual cannot be identified. Conversely, no identifiable information on any individual will be released to anyone other than project personnel without a signed medical release from the subject, or where appropriate, the next of kin or a physician in case of a life-threatening emergency to the subject. All project personnel will be instructed not to discuss any cases with persons other than project personnel.

For this specific project, it may be required to collect PHI such as age, DOB, Medical Record Number and dates of diagnoses. Only the study team will have access to this data, and it will not be shared with anyone outside of the study team. Data will be collected on paper source documents and transcribed into the GSM REDCap system. Only study team members will have access to the database. The database will utilize the study number assigned and will not include the subject's name or MRN. All subjects will have an assigned number. All completed paper forms will be kept in locked files in locked rooms to which only project personnel have access.

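### The randomization procedure is largely unspecified, nothing protects balance on CT calcium arc, and adjusting only for significant baseline differences would miss most chance imbalances in it

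*Combined protocol and SAP*

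**What the plan says.** Section 4.3.3: "The patient will be randomized using a randomized generator to either Group 1 (intervention) or Group 2 (control". Nothing else in the document describes how the sequence is made, who holds it, or when it is revealed.

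The intended result is stated. Section 3.3: "We plan to enroll up to a total of 100 patients, 50 patients in each group". Section 9.1 assumes equal allocation.

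Calcium enters the design twice, both times as eligibility. Section 3.4.1 includes "Patients with > 90-degree arc of calcium at the large bore access site per CT documentation", with no upper limit and no severity categories. Section 3.4.2 excludes "Unfavorable calcium distribution of femoral artery", with no working definition.

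Chance imbalance is handled afterwards. Section 9.2 tests baseline characteristics between arms and carries the significant ones into a logistic regression for the primary outcome. Calcium arc is not named as a covariate.

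**The concern.** Patients enter with any arc above 90 degrees, so severity can vary widely within the trial. It is plausibly related to access site complications, the primary outcome. The plan does not stratify on it and does not commit to adjusting for it. Adjustment depends on a baseline significance test, which at 50 per arm responds only to large gaps. A moderate imbalance would therefore stay in both the crude comparison and the adjusted one. Section 9.1 says the effect size found here will be used to power a larger trial, so an avoidable distortion would carry forward.

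The second part is missing detail. The study team screens, one calcium exclusion is a matter of judgement, and no blinding is described. A reader therefore cannot verify from the text that eligibility is settled before the assignment can be known.

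**Working it through.** **1. The plan's own figure.** Inputs from section 9.1: "sample size calculation was performed using a 20% reduction", "with a two-tailed hypothesis, a power of 80%, and an equal allocation ratio to treatment arms". From section 9.2: "statistical significance will be assumed at an alpha value of 0.05". No control-arm rate is given, and absolute or relative reduction is not stated, so a rate has to be assumed.

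n per arm = [1.96·√(2p̄(1−p̄)) + 0.842·√(p₁(1−p₁)+p₂(1−p₂))]² / (p₁−p₂)²

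For 25% v 5%: (1.96·√0.255 + 0.842·√0.235)² / 0.04 = 48.8, so 49 per arm and 98 in total, close to the stated 100. Other assumptions do not match: 30% v 10% gives 124, 40% v 20% gives 164, and a relative 20% reduction from 30% gives 1,718. The 25% v 5% case is used below as an illustration only.

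**2. Arm sizes, if randomization is simple.** Binomial(100, 0.5): exactly 50:50 in 8.0% of trials, 45:55 or closer in 72.9%, 40:60 or closer in 96.5%. Power at 25% v 5%:
- 50:50: 80.9%
- 45:55: 79.7-81.4%, depending on which arm is larger
- 40:60: 77.6-81.2%

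The worst loss at 40:60 is 80.9 − 77.6 = 3.3 points (at 30% v 10%: 71.1 − 67.4 = 3.7). This is minor.

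**3. Balance on calcium.** Assume a binary severity factor with prevalence f of 30% or 50%; the documents give no distribution. Simulated share of trials (200,000 draws):

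| Gap between arms | Simple, f = 30% | Simple, f = 50% | 50:50 without strata, f = 30% | 50:50 without strata, f = 50% |
|---|---|---|---|---|
| ≥10 points | 28.7% | 36.7% | 27.7% | 31.8% |
| ≥15 points | 10.5% | 13.3% | 12.7% | 16.2% |
| ≥20 points | 3.0% | 5.7% | 4.8% | 7.1% |

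Fixing the arm sizes does not balance calcium; only stratification does.

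**4. What the baseline test would catch.** The standard error of the gap at 50 per arm is √(f(1−f)·2/50), which is 9.2 points at 30% and 10.0 at 50%. Significance needs 1.96 times that: 18.0 and 19.6 points. Example: 24/50 v 16/50 is a 16-point gap; z = 0.16/√(0.4·0.6·0.04) = 1.63, p = 0.10, so no adjustment follows.

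With exact 50:50 arms and whole patients, the smallest significant gap is 20 points (20 v 10 when 30 patients have the factor, 30 v 20 when 50 do). Of gaps of at least 10 points, the share missed is 1 − 4.8/27.7 = 83% at f = 30% and 1 − 7.1/31.8 = 78% at f = 50%. Under simple randomization it is about 82-84%. These use the uncorrected chi-square.

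**5. Effect on the primary comparison.** Shift in the crude risk difference = imbalance × difference in complication risk across the factor. That difference is not in the documents. With an assumed 25 points (35% v 10%), a 15-point imbalance shifts the result by 0.15 × 25 = 3.75 points, and a typical imbalance of about 6 points by 0.06 × 25 = 1.5. With an assumed 10 points, the 15-point imbalance shifts it by 1.5.

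For scale, the standard error of the risk difference at 50 per arm is √(0.25·0.75/50 + 0.05·0.95/50) = 6.9 points (7.7 at 30% v 10%). The 3.75-point case is about half a standard error.

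**6. After stratified blocking, two strata.** An unfinished block leaves an excess of at most 2 (block of 4) or 3 (block of 6) in each stratum. The calcium gap is then at most about 2/50 = 4 or 3/50 = 6 points, and the arms are at worst 48:52 or 47:53.

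**The case against.** The strongest reply is that the text is silent rather than wrong. A reader might infer that the generator is unrestricted, that allocation is not concealed, or that 50 per arm will not be reached. None of these is stated. A generator can produce a blocked list, and section 9.1 assumes equal allocation. Silence shows only that the method is undescribed.

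A reader might also infer that the calcium exclusion will be applied with the assignment known. The documents point the other way. Section 4.2 lists CT review and the eligibility review, then enrols those who meet all criteria; sections 4.3.1 and 5.1 also put screening before enrolment; randomization first appears later, under administration of the intervention. The order relative to assignment is never stated outright, but no breach is shown. Section 9.2 makes inferential analyses intention-to-treat, and section 3.5 keeps data on patients who leave after enrolment. What remains is the possibility of foreknowledge before entry, which intention-to-treat cannot repair and one sentence would close.

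It can fairly be added that simple randomization of 100 patients is valid, that chance imbalance is already reflected in the confidence interval, and that logistic regression is planned. All of this stands. It does not rescue the rule for choosing covariates, which responds to the size of a chance gap rather than to prognostic importance and would miss most gaps of 10 points or more.

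Finally, blocking has a cost that simple randomization lacks: at a single centre where treatment is visible, the last assignments in a block can be partly guessed. Varying the block size reduces this but does not remove it.

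**Conclusion.** The point holds as a design improvement plus a gap in description. Nothing in the plan protects balance on calcium arc. If randomization is simple, gaps of at least 10 points on a factor present in 30-50% of patients arise in about 29-37% of trials, and the significance rule would leave roughly four in five of them unadjusted. The prevalence and the risk gradient are assumptions; the likely shift in the result is modest, about 1.5 to 4 points on the gradients tried.

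This is avoidable chance error. It is not evidence of bias, and the documents do not support a claim that allocation is unconcealed. Arm-size inequality is not a reason to change anything by itself. The change is worthwhile because it is cheap and because concealment and stratification cannot be added after enrolment.

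**What to change.** In section 4.3.3, state that patients are randomized 1:1 in permuted blocks of randomly varied size (for example 4 and 6), stratified by CT calcium arc in two levels whose cut-point the investigators set in advance. In section 9.2, include the arc stratum as a prespecified covariate in the primary logistic model, whatever the baseline test shows, alongside the unadjusted odds ratio already planned.

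Also state that the list is prepared by someone outside enrolment, and that assignment is revealed only after every eligibility criterion, including calcium distribution, has been recorded. Any concealed method would do. The database might serve, but section 11.1 says only "Data will be collected on paper source documents and transcribed into the GSM REDCap system", which does not show that it is set up for allocation.

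Cost: about one paragraph and minor set-up, since the arc is already read from the pre-procedure CT to establish eligibility. The model gains one term; at the assumed 25% v 5% there would be about 50 × 0.25 + 50 × 0.05 = 15 events, which can carry treatment and one stratum term but leaves little room for more. Assignments at the end of blocks become slightly predictable, so the block sizes should not be disclosed to the enrolling team.

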5. RISK

5.1 Physical Risks

Although the procedure approach being used in this protocol has been well tested for efficacy and safety, there may be potential risks associated with participation. Any medical treatment can have temporary and permanent side effects and can cause unforeseen adverse reactions, intolerance, or worsening of co-morbidities, which could lead to acute adverse event such as worsening kidney disease, allergic/immunologic reaction, infections, vascular complications, stroke, or death. All of which are risks associated with the TAVR procedure itself and are of low probability and discussed in detail prior to the TAVR procedure. With any invasive procedure, there may be unforeseeable risks associated with the procedure resulting in complications or physical harm. Any subject with known medical conditions, or on a concurrent medication in which the study intervention is not recommended, will be excluded from participation.

The intervention used in this study are currently in common use and will be administered in accordance with current standards (ultrasound and fluoroscopy-guided vascular access, modified Seldinger technique) which are put forth in attempts to mitigate any potential risks. Patients will be carefully screened for contraindications to participation prior to study enrollment. We will monitor for adverse events in enrolled patients.

